### Study Design

Study Type: Interventional (Clinical Trial)

Estimated Enrollment: 90 Participants

Allocation: randomized

Interventional Model: Parallel assignment

Masking: None (Open Label)

Experimental (subgroups)	Intervention / treatment (device)
Cytokine adsorber filter will be installed into the (hemodialysis or cardiopulmonary bypass (CPB) (15 patients on ECMO)	Cytokine adsorber is a biocompatible, high adsorptive polymer indicated in conditions where cytokine levels are extremely elevated.
Cytokine adsorber filter will be installed into the (hemodialysis or cardiopulmonary bypass (CPB) (15 patients with sepsis)	Cytokine adsorber is a biocompatible, high adsorptive polymer indicated in conditions where cytokine levels are extremely elevated.
Extracorporeal hemoperfusion cartridge will be installed into the (hemodialysis or cardiopulmonary bypass (CPB) (15 patients on ECMO)	Extracorporeal hemoperfusion cartridge is a biocompatible, high adsorptive polymer indicated in conditions where cytokine levels are extremely elevated.
Extracorporeal hemoperfusion cartridge will be installed into the (hemodialysis or cardiopulmonary bypass (CPB) (15 patients with sepsis)	Extracorporeal hemoperfusion cartridge is a biocompatible, high adsorptive polymer indicated in conditions where cytokine levels are extremely elevated.
Control (subgroups)	
No filter will be installed into the ECMO in	

this study group (15 patients)	
No filter will be installed into the patient with sepsis (15 patients)	

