#### Secondary outcomes

1. Ventilator free days (VFD) [Time Frame: 30 days]

Ventilator free days (VFD) in the first 30 days after randomization, where invasive mechanical ventilation (IMV), non-invasive ventilation (NIV) and ECMO are defined as ventilator days. VFD=0, if the patient dies in the first 30 days after randomization

2. Time to extubation from ventilation and explantation from ECMO [ Time Frame: 30 days ]

Time to extubation from ventilation and explantation from ECMO. Death under ventilation and/or ECMO will be analyzed as a competing event. The time will be censored at the time of last visit for surviving patients under ventilation and/or ECMO.

3. Difference of d-dimers [Time Frame: 24, 48, 72 hours]

Comparison to enrollment or between 3 groups at 24, 48, 72 h

4. Difference of Serum lactate [Time Frame: 24, 48, 72 hours]

Comparison to enrollment or between 3 groups at 24, 48, 72 h

5. SOFA-Score [Time Frame: 24, 48, 72 hours]

Sequential Organ Failure Assessment Score at 24, 48, 72 h (values from 6 to 24, where the higher values explain higher disease severity)

6. Serious adverse device effects [Time Frame: 30 days]

Serious complications or malfunctions related to the CytoSorb device

7. Adverse event of special interest: air in the ECMO system [Time Frame: 30 days]

- Unintended air in the ECMO system during operation of the device
- 8. Adverse event of special interest: blood-clotting in the ECMO system [Time Frame: 30 days]
  - Unintended blood-clotting in the ECMO system during operation of the device
- 9. Adverse event of special interest: bleeding complications [Time Frame: 30 days]
  - Major bleeding events

*Patient with septic shock*

- 1. Difference of Cytokine response [ Time Frame: 24-48 hours of septic shock ]
  - Cytokine response: Level of procalcitonin, Level of C-reactive protein, Level of interleukin-1, Level of interleukin-6, Level of interleukin-8, Level of interleukin-10, Level of Tumor Necrosis Factor-  $\alpha$  at 24, 48 hours.

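### Serious device effects are tied to one named product, and ECMO-circuit air and clotting to an undefined device; if that device is the adsorber, these outcomes have no usable control rate

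*Combined protocol and SAP*

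**What the plan says.** The harm outcomes for ECMO patients are items 6 to 9 of the list headed Secondary outcomes, each with a 30-day time frame.

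- **Item 6**, serious adverse device effects: "Serious complications or malfunctions related to the CytoSorb device".
- **Item 7**, air: "Unintended air in the ECMO system during operation of the device".
- **Item 8**, clotting: "Unintended blood-clotting in the ECMO system during operation of the device".
- **Item 9**, major bleeding, with no condition about a device.

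The Study Design table in section 4 gives six subgroups of 15. Two ECMO subgroups receive an adsorber: one the cytokine adsorber, the other the hemoperfusion cartridge. The third is the control: "No filter will be installed into the ECMO". The column describing the adsorber and the cartridge is headed "Intervention / treatment (device)".

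The Statistical studies section lists Fisher's exact test and the chi-square test for qualitative data. It does not say how safety events are to be compared between arms.

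**The concern.** A randomised control arm shows how often a harm occurs without the intervention. That works only if events are counted by the same rule over the same period in every arm. Air and clotting can arise in any ECMO circuit, with or without a filter. If they count only while a filter is running, control patients have no period in which an event can count. The background rate of circuit problems is then charged entirely to the adsorbers. In the other direction, an adsorber patient whose circuit clots after the filter is removed is not counted, although the outcome has a 30-day frame.

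Item 6 has a separate problem that does not depend on how items 7 and 8 are read. It requires attribution to one named product, so controls cannot contribute, and neither can the cartridge arm if the words are taken as written.

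At stake are two of the plan's own adverse events of special interest and its only serious-device-effect outcome, in an open-label trial whose results are meant to support national clinical protocols.

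**Working it through.** **Which device?** Items 7 and 8 allow two readings.

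| Reading | Support in the text | Consequence for ECMO controls |
|---|---|---|
| Adsorber or cartridge | Item 6, just above, speaks of the CytoSorb device. The design table uses the word for the adsorber and cartridge. Items 7 and 8 name the ECMO system and then, separately, the device. The septic-shock secondary outcomes also time samples by the start and end of the adsorber. | No period at risk: 0/15 by definition |
| ECMO system | The event is located in the ECMO system. The abstract speaks of mechanical support devices. | Controls are scored and the structural zero disappears |

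The first reading is likelier, but the text does not settle it.

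**Inputs.** From the Study Design table: 15 ECMO patients per arm. The enrolment arithmetic agrees: 6 × 15 = 3 × 30 = 90. The plan states no event rate, significance level, power or filter run time, so there is no figure of its own to reproduce. The following are assumptions: two-sided 0.05, true event rates r of 10 to 40%, and no added risk from either device.

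**Rejection thresholds against a fixed 0/15** (Fisher's exact test, two-sided):

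- One device arm v control: 4/15 gives p = 0.100 and 5/15 gives p = 0.042, so at least 5 events are needed.
- Both device arms pooled v control: 7/30 gives p = 0.077 and 8/30 gives p = 0.038, so at least 8 events are needed.

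**Chance of a false harm signal on the adsorber reading**, with the filter running for the whole ECMO period. This is P(X ≥ 5) for X ~ Bin(15, r), or P(X ≥ 8) for X ~ Bin(30, r):

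| r in every arm | Apparent excess | 15 v 15 | 30 v 15 (pooled) |
|---|---|---|---|
| 10% | +10 points | 1% | 1% |
| 20% | +20 points | 16% | 24% |
| 30% | +30 points | 48% | 72% |
| 40% | +40 points | 78% | 96% |

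The true excess is zero in every row. The pooled column applies only if the device covers both products. If it is CytoSorb alone, the cartridge arm is also zero by construction and only the 15 v 15 column is relevant.

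**Shorter filter run.** If the filter runs for a share f of the ECMO period at constant hazard, the scored rate is 1 − (1 − r)^f. With f = 0.5, the scored rates for r = 10, 20, 30 and 40% are 5.1, 10.6, 16.3 and 22.5%. The chance of a false signal at 15 v 15 falls to 0.1, 1.6, 8.4 and 24%. The share of affected patients who go uncounted rises: at r = 40%, 22.5 of 40 points are scored and 17.5 are lost.

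**One common window in all arms.** The expected difference returns to zero. Over the same rates, the false-positive rate is 0.5 to 1.7% (15 v 15) or 2.1 to 3.3% (30 v 15). Precision stays poor. For 20% v 40%, Fisher power is 11% (15 v 15) or 21% (30 v 15). The 95% interval half-width at 15 v 15 is 1.96 × √(0.2 × 0.8/15 + 0.4 × 0.6/15) = 0.32, or 32 points.

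**The case against.** The strongest reply is that this is one undefined word. Items 7 and 8 place the event in the ECMO system, which controls have. If the device is the ECMO system, controls are scored, and events after filter removal are counted while ECMO continues. This stands to the extent that a reader who infers that controls certainly cannot score air or clotting goes further than the documents allow. The structural zero is conditional on the likelier reading. The ambiguity is still a fault, because open-label staff could record the same event in one arm and not in another.

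Second, a reader might infer that the plan cannot estimate any excess harm from the adsorbers. The documents do not support that. Major bleeding carries no device condition. Section 4 says that perioperative complications and survival will be documented, without limiting this to device arms. D-dimers are listed for comparison between the three groups, survival runs from randomisation, and 72-hour mortality is an outcome. All of these can be compared with control.

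Third, device-attributed effects never have a control rate, so item 6 is not wrong merely for being attributed. That is correct. What is missing is an all-cause count beside it, and the second device.

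Fourth, the size rests on assumed rates, and pooling the device arms is not in the plan. Both are true. At a 10% rate, or with a short filter run, a false signal is unlikely.

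**Conclusion.** The point holds for items 6 to 8 only. Item 6, on any reading, gives no control rate and as worded leaves out the cartridge arm. Items 7 and 8 do not define the device. If it is the adsorber, the air and clotting contrasts with control are not interpretable: controls are zero by construction and events after filter removal are dropped.

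The false-signal range of about 1 to 78% at 15 v 15 (1 to 96% if pooled) illustrates the bias and does not forecast it. It depends on the assumed event rates, a two-sided 0.05 test, equal true risk, and a filter that runs throughout ECMO. The bias does not depend on significance testing, since the apparent excess equals the scored background rate whatever test is used. The primary cytokine outcome is unaffected. The point still goes beyond missing detail, because following the wording on its likelier reading would build unequal counting into the safety comparison, and control events that were never recorded may not be recoverable.

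**What to change.** 1. In items 7 and 8, drop the condition about the device operating. Count events at any time from randomisation to ECMO explantation or day 30, whichever is first, in all three ECMO arms. State that death on ECMO also ends the window.
2. Report, by arm, the number of patients with an event and the rate per ECMO-day. ECMO time should be derivable from secondary outcome 2, which already follows patients to explantation.
3. In item 6, name both devices. Add all-cause serious adverse events in all three arms, with device attribution as a sub-tabulation.
4. Present these outcomes as estimates with confidence intervals. At 15 per arm, a non-significant test is no evidence of safety.

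The cost is three reworded definitions, one added table and somewhat more event recording in controls. The documents do not say whether circuit events are recorded routinely in control patients, so this should be checked. No treatment changes. The fix makes the contrast interpretable, but it does not make it well powered.

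### Air and clotting are counted only in the ECMO system, but the arm table places the devices in hemodialysis or CPB, so some device-circuit events may go uncounted

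*Combined protocol and SAP*

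**What the plan says.** The Study Design table in section 4 has six subgroups of 15 patients. Its rows for the two ECMO device subgroups read "Cytokine adsorber filter will be installed into the (hemodialysis or cardiopulmonary bypass (CPB) (15 patients on ECMO" and "Extracorporeal hemoperfusion cartridge will be installed into the (hemodialysis or cardiopulmonary bypass (CPB) (15 patients on ECMO". The septic rows use the same installation wording, for example "Cytokine adsorber filter will be installed into the (hemodialysis or cardiopulmonary bypass (CPB) (15 patients with sepsis". No device row names the ECMO circuit. The ECMO control row, however, begins "No filter will be installed into the ECMO in", which suggests that the ECMO circuit is where the filter would otherwise go.

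Four items in the Secondary outcomes list for ECMO patients bear on harm, each with a 30-day time frame:

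- Item 6: "Serious complications or malfunctions related to the CytoSorb device".
- Item 7: "Unintended air in the ECMO system during operation of the device".
- Item 8: "Unintended blood-clotting in the ECMO system during operation of the device".
- Item 9: "Major bleeding events".

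Section 4 also says that perioperative complications will be documented, but it does not define them or tie them to a circuit.

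**The concern.** Items 7 and 8 are the only listed outcomes that count circuit air and clotting without asking anyone to judge whether the device was the cause. In an open-label trial that makes them valuable. Their scope is the ECMO system, whereas the device rows describe a hemodialysis or CPB installation. If an adsorber or cartridge is run in its own hemodialysis line, clotting or air in that line is the most direct form of added circuit harm, yet read literally it meets neither definition. What is at stake is whether the safety comparison can see the harm that an extra circuit would add.

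**Working it through.** The plan states no event rate, power or sample size for circuit events, so there is no figure of its own to reproduce. The subgroup counts agree with the stated enrolment: 6 × 15 = 90. Of the 3 × 15 = 45 ECMO patients, 2 × 15 = 30 are in device arms.

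**Step 1. Which item takes an air or clotting event in an ECMO patient, read literally?**

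| Where the event occurs | Cytokine adsorber arm | Hemoperfusion cartridge arm |
|---|---|---|
| ECMO system | Items 7 or 8 | Items 7 or 8 |
| Separate hemodialysis circuit, serious and judged device-related | Item 6 | No named item |
| Separate hemodialysis circuit, not serious or not judged related | No named item | No named item |

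Item 9 takes major bleeding in any circuit, but that is a different event. The general recording of complications is not a defined air or clotting outcome.

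**Step 2. How much could items 7 and 8 miss?** The inputs are assumptions. Let p be the true proportion of patients with an event in one 15-patient device subgroup, and f the share of those events outside the ECMO system. Expected counted events = 15 × p × (1 − f). The chance of counting at least one = 1 − (1 − p(1 − f))^15.

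| p | f = 0 | f = 25% | f = 50% | f = 100% |
|---|---|---|---|---|
| 10% | 1.5; 0.794 | 1.125; 0.689 | 0.75; 0.537 | 0; 0 |
| 20% | 3.0; 0.965 | 2.25; 0.913 | 1.5; 0.794 | 0; 0 |
| 30% | 4.5; 0.995 | 3.375; 0.978 | 2.25; 0.913 | 0; 0 |

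Each cell gives expected counted events, then the chance of at least one.

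**Step 3. What happens to the comparison with control?** Assume 15% ECMO-circuit clotting in every arm, an independent added risk c in the adsorber circuit, and a share h of devices in a separate circuit.

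- Any-circuit risk = 1 − (1 − 0.15)(1 − c). For c = 10%, 20% and 30% this is 23.5%, 32.0% and 40.5%. The true excess over control is 8.5, 17 and 25.5 points.
- Counted risk = h × 15% + (1 − h) × any-circuit risk, so the counted excess is (1 − h) times the true excess:
  - h = 0: 8.5, 17 and 25.5 points (nothing lost).
  - h = 0.5: 4.25, 8.5 and 12.75 points.
  - h = 1: 0 points.

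**Step 4. Does the direction hold?** Step 3 needs controls to be able to score. That is so if the device named in items 7 and 8 is the ECMO machine. If it means the adsorber, controls count 0%, and at h = 1 the counted excess is at most 15 − 0 = 15 points. Against the true excess, 15 points is 15 − 8.5 = 6.5 too high at c = 10%, 17 − 15 = 2 too low at c = 20%, and 25.5 − 15 = 10.5 too low at c = 30%. The sign is therefore not fixed.

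If a share d of controls is also dialysed, with the same risk c, the true excess at h = 1 falls to 0.85 × c × (1 − d).

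**The case against.** The strongest reply is that the premise is unsettled. Section 3 describes ECMO as a prolonged form of cardiopulmonary bypass, so CPB in the ECMO rows may simply mean the ECMO circuit, and the control row supports that reading. The same phrase in the septic rows suggests a generic list of access options. Nor does the plan say whether a connected dialysis line belongs to the ECMO system. This stands as far as the CPB option goes. It does not remove the hemodialysis option, and section 3 elsewhere lists CPB and ECMO separately and describes veno-venous hemofiltration added alongside ECMO.

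A reader might infer that device-circuit events are not scored at all and that device harm is understated. The documents do not support that. Item 6 takes serious CytoSorb-related events in any circuit, and item 9 takes major bleeding. Nothing in the plan generally bars dialysis in ECMO controls, who could then have uncounted events too. As Step 4 shows, the direction of any bias also depends on what the word device refers to.

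It is also fair to say that air or clotting in the ECMO circuit is a legitimate safety outcome in its own right. That is a reason to keep those counts and add to them, not to replace them.

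**Conclusion.** The inconsistency is real and should be corrected. If a device runs in a separate hemodialysis circuit, air or clotting there may go uncounted by items 7 and 8. For the cytokine adsorber, the remaining gap is events that are not serious or not judged related. For the hemoperfusion cartridge, planned in 15 of the 30 device-arm ECMO patients, even a serious event has no named item.

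Device-circuit harm may therefore be under-counted. The size cannot be determined from the documents: it runs from nothing, if every device sits in the ECMO circuit, to every device-circuit air or clotting event missed by items 7 and 8, if every device runs separately. The rates in the working are assumptions that show the mechanism. They are not estimates for this trial.

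**What to change.** 1. Reconcile the device rows, the control row and items 7 and 8 on which circuit carries the device, and say what the ECMO system includes. This point takes no view on which circuit should be used.
2. Keep the ECMO-circuit counts. Add air, and clotting, in any extracorporeal circuit (ECMO, hemodialysis or CPB) over 30 days from randomisation in all arms, with the circuit recorded on the case report form. Counting in all arms keeps the comparison fair if controls are dialysed.
3. Replace the restriction to device operation with an observation window that applies equally to controls.
4. Extend item 6 to both devices.

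The cost is revised outcome wording and one extra case-report field. Event rates in the device arms may look less favourable.

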**Secondary Outcome Measures:**

- 1. Inflammatory reaction [Time Frame: 6 - 24 hours]
  - Level of C reactive protein (CRP), white blood cells and procalcitonin immediately after induction of anesthesia, before initiation of adsorber, 2 hours after initiation of adsorber, at termination of adsorber, 6-12-24 hours after wean of adsorber.
- 2. Difference of serum interleukin-6 level [Time Frame: 48, 72 hours]
  - Comparison to enrollment or between 3 groups at 48, 72 h
- 3. Difference of serum interleukin-1 $\beta$  level [Time Frame: 24, 48, 72 hours]
  - Comparison to enrollment or between 3 groups at 24, 48, 72 h
- 4. Difference of serum interleukin-10 level [Time Frame: 24, 48, 72 hours]
  - Comparison to enrollment or between 3 groups at 24, 48, 72 h
- 5. Difference of serum procalcitonin level [Time Frame: 24, 48, 72 hours]
  - Comparison to enrollment or between 3 groups at 24, 48, 72 h

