#### **4. Research methods and ethical issues**

Patients before implantation of ECMO and/or patients with sepsis will be enrolled in the study after giving a written, signed informed consent.

The participants will be randomized into 3 groups:

- **Intervention group #1** a cytokine adsorber will be used (30 patients): patients on ECMO – subgroup A; septic patients – subgroup B.
- **Intervention group #2** an extracorporeal hemoperfusion cartridge will be used (30 patients): patients on ECMO – subgroup C, septic patients – subgroup D.

- **Control group #3** without using extracorporeal adsorber (30 patients): patients on ECMO subgroup - E, septic patients - subgroup F.

The investigators will collect demographic, clinical and laboratory data about patients before, during and after the operation

The incidence of early cellular or humoral rejection, length of ventilation, ICU and hospital stay, the use of vasopressors and inotropes in the perioperative period and incidence of perioperative complications and survival will be documented.

The level of cytokines (IL-1, IL-6, IL-8, IL-10, tumor necrosis factor-alfa) and complements before, during and after the use of ECMO, patients with sepsis will be determined if the investigators find relevant difference between the two groups in clinical variables.

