### Statistical studies

1) Statistical data processing

2) Comparison and analysis of source data

After data receiving, statistical analysis will be performed using SPSS Statistics software version 22. For quantitative data, the Mann-Whitney Yu non-parametric test and parametric t-test will be performed, and Fisher's non-parametric exact test and  $\chi^2$  parametric test will be performed for qualitative studies. Also, a logistic regression for categorical outcomes and a survival analysis (non-parametric Kaplan-Meier and parametric Cox regression) will be performed.

**Ages:**18 Years and older

**Sex:** All

**Accepts healthy volunteers:** No

Groups	Inclusion criteria	Exclusion Criteria:
ICU patients with ECMO	

• Hemodynamic support with vasopressors

• Procalcitonin level <math>\geq 1</math> ng/ml

• Invasive hemodynamic monitoring

• Written informed content

	

• age <math>< 18</math> years

• acute liver or kidney failure straight before transplantation

• the patient declines participating in the study

ICU patients with septic shock of medical origin	

• Signs of hypoperfusion: serum lactate <math>>2</math> mmol/L, low central venous oxygen saturation (ScvO2) (<math><70\%</math>) or high ScvO2 (<math>>85\%</math>), metabolic acidosis, oligo-anuria,

	

• Patients under 18 years

• Pregnancy (bHCG test positivity)

• Surgical intervention in context with the septic insult

	
high venous-to-arterial CO2-gap (dCO2 >6 mm Hg)
 
 
• Hemodynamic support with vasopressors
 
• Procalcitonin level <math>\geq</math> 1 ng/ml
 
• Invasive hemodynamic monitoring
 
• Written informed content
 
	
New York Heart Association IV heart failure
 
 
• Acute coronary syndrome
 
• Acute haematological malignancies
 
• Immunosuppression, systemic steroid therapy (>10mg prednisolon/day)
 
• Human immunodeficiency virus infection (HIV) and active AIDS
 
• Patients with donated organs
 
• Thrombocytopenia (<20.000/ml)
 
• More than 10%-of body surface area with third degree burn
 

--	---	--

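### Septic inflammatory-reaction outcome (CRP, white cells, procalcitonin): every sampling time hangs on the adsorber or on anaesthesia, so septic controls have no guaranteed sample

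*Combined protocol and SAP*

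**What the plan says.** The list headed Secondary Outcome Measures follows the sub-heading "Patient with septic shock", so by order of headings it belongs to the septic cohort. Its first item is "Inflammatory reaction [Time Frame: 6 - 24 hours"], and the analytes are given as "Level of C reactive protein (CRP), white blood cells and procalcitonin". The sampling times are "immediately after induction of anesthesia, before initiation of adsorber, 2 hours after initiation of adsorber, at termination of adsorber, 6-12-24 hours after wean of adsorber".

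The Study Design table says of the septic control subgroup: "No filter will be installed into the patient with sepsis (15 patients"). Section 4 (Research methods and ethical issues) describes the whole control group as "without using extracorporeal adsorber (30 patients"). The eligibility table under Statistical studies defines the cohort as "ICU patients with septic shock of medical origin" and lists among its exclusions "Surgical intervention in context with the septic insult".

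No section gives controls a substitute clock, such as hours from randomisation or a notional start and stop time. No section states how long the adsorber runs.

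**The concern.** A between-arm comparison needs a time that exists in every arm. Here the times exist only where there is a device or an induction of anaesthesia. The septic controls have no device, and nothing in their pathway calls for an induction. Following the text literally therefore gives no device-versus-control result for this outcome.

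A fall in a marker within a device arm cannot be separated from natural recovery, so within-arm change is a weak substitute. The trial is also open label. If staff invent times for controls, the choice is made with the arm known, and sampling time then differs systematically by arm. A control sample that was never scheduled cannot be recovered at analysis.

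**Working it through.** The plan gives no figure to reproduce. The check is a count of the times, followed by a comparison with neighbouring outcomes.

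**1. Count by anchor** (Secondary Outcome Measures, item 1)

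| Anchor | Times | Number |
|---|---|---|
| Induction of anaesthesia | just after induction | 1 |
| Adsorber start | before it, and 2 h into treatment | 2 |
| Adsorber stop | when it ends | 1 |
| Adsorber removal | 6, 12 and 24 h later | 3 |
| Randomisation, enrolment or shock onset | none | 0 |

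Total 1 + 2 + 1 + 3 = 7, of which 2 + 1 + 3 = 6 depend on the adsorber.

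**2. Apply to the septic arms** (Study Design table: 15 + 15 + 15 = 45)

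- Adsorber and cartridge arms: six device-timed samples each, reading the word adsorber to cover both devices.
- Controls: 0 of 6 device times. The induction time is not guaranteed, because the cohort is medical and surgery for the septic insult is excluded. Guaranteed samples: 0 of 7, for 15/45 = one third of the cohort.

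**3. Compare with the ECMO primary outcome.** It has nearly the same pattern: before the start, 2 h in, at removal, then 6, 12 and 24 h later. It is tied to ECMO itself, which all three ECMO subgroups receive. The septic item ties that pattern to a device that one arm never has.

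**4. What septic controls have elsewhere**

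| Marker | Before 24 h | 24 h | 48 h | 72 h |
|---|---|---|---|---|
| Procalcitonin | no listed follow-up | yes | yes | yes |
| CRP | no | yes | yes | no |
| White cells | no | no | no | no |

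The CRP entries, and procalcitonin at 24 and 48 h, come from the septic cytokine-response item. Procalcitonin at 24, 48 and 72 h comes from item 5, which allows comparison among the three groups.

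**5. Effect of improvised control times.** Suppose controls were sampled at h hours from randomisation and device patients at h hours after removal. Let d be the delay to device start and r the run length. Device patients are then sampled at d + r + h hours and controls at h, a gap of d + r. The documents give neither d nor r, and no rule for controls. If the marker is falling, the gap flatters the devices; if it is rising, it counts against them.

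**The case against.** - **Item 1 never promises a three-group comparison.** Items 2 to 5 do and item 1 does not, so it could be meant as device-period kinetics. That is a possible reading, but the text does not say so. In a randomised trial with a no-device arm, the intended comparison should be stated.
- **Controls are already well covered.** This largely stands. CRP and procalcitonin have control values at 24 and 48 h, and procalcitonin also at 72 h. The procalcitonin entry criterion (at least 1 ng/ml) implies a value near enrolment as well. A reader might infer that Subtasks 2.2 and 2.3 (immune response with each device in sepsis) cannot be answered; the documents do not support that.
- **White cells may still be recorded.** Section 4 collects laboratory data in general, without limiting it to device arms. It names neither white cells nor times, so the accurate statement is that they appear in no other listed outcome, not that they go unmeasured in controls.
- **Some controls may be anaesthetised for another reason.** True, since the exclusion covers only surgery linked to the septic insult. The statement is therefore that no sample is guaranteed, not that none could occur. Such a sample would at most be a baseline, as would a generous reading of the time before adsorber start. Neither gives controls a follow-up value.
- **The printed frame of 6 to 24 hours supplies a clock.** It has no origin, and the item itself counts 6, 12 and 24 h from device removal.
- **The list may not be septic only.** Its population rests on heading order. If it also covered ECMO patients, the six adsorber times would be undefined for all 30 controls.

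**Conclusion.** The point holds as a narrow gap in the definition of one secondary outcome. Septic controls have 0 of 7 guaranteed samples, so as written the outcome supports only adsorber versus cartridge or within-arm change. The loss is every listed control comparison of white cells, and of CRP and procalcitonin before 24 h.

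A reader might go further and infer a bias of known size favouring the devices. The documents do not support this: it would need a rule for control times, a run length and a rate of marker decline, none of which they contain. What can be said is that improvised times would confound timing with arm, in a direction that depends on the marker's course.

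The conclusion assumes that the list belongs to the septic cohort and that controls receive no device, as the Study Design table states. It depends on no assumption about power or effect size. Grade: should fix, before sampling.

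**What to change.** Define the between-arm comparison on one clock starting at randomisation in all three septic arms:

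- Sample at, for example, baseline (before any device), 2, 6, 12 and 24 h. Continue at the times already listed: 48 h for CRP and procalcitonin, 72 h for procalcitonin. Add white cells at 48 and 72 h if wanted; they are not listed there now.
- State the clock origin for those existing samples too. The septic cytokine-response item counts hours of septic shock, while item 5 refers to enrolment.
- Delete the anaesthesia sample.
- Record adsorber start and stop times. Treat any samples at or after device removal as descriptive, in the device arms only.

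The change amends one outcome definition and the sampling sheet and alters no treatment. It is not free of extra blood draws. Controls go from no guaranteed time for this outcome to five; the 24 h draw can coincide with one already listed if the clocks are aligned. Device patients go from seven times to five, or up to 5 + 4 = 9 if the four samples at and after removal are kept. Kinetics after removal become descriptive.
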